3 STATISTICAL AND ANALYTICAL PROCEDURES

3.1 ANALYSIS ENDPOINTS

3.1.1 Demographic and baseline characteristics

Unless otherwise specified, the baseline value is defined as the last available value obtained up to the first double-blind IMP injection.

For patients randomized and not treated, the baseline value will be the last available value on or before the day of randomization.

All baseline safety and efficacy parameters (apart from those listed below) will be presented along with the summary statistics in the safety and efficacy sections (Section 3.4.5 and Section 3.4.4).

Demographic characteristics

Demographic variables are:

- Age in years (quantitative and qualitative variable: <65, ≥65 to <75, and ≥75 years; and <65, ≥65 years);
- Gender (Male, Female);
- Race (White, Black or African American, Asian, American Indian or Alaska Native, Native Hawaiian or other Pacific Island, other);
- Ethnicity (Hispanic or Latino, Not Hispanic or Latino);
- Region (North America, South America, Western Europe, Eastern Europe, Asia, Rest of the world as defined in Section 3.5.6).

Medical or surgical history

This information will be coded using the version of Medical Dictionary for Regulatory Activities (MedDRA) currently in effect at Sanofi at the time of database lock.

Medical or surgical history includes:

- Medical history of allergies;
- Patient's family medical allergic history;
- Other relevant medical or surgical history;
- Smoking habits;
- Alcohol habits.

Medical history of specific interest includes:

- Coronary artery disease history prior to the index ACS event;
- Cardiovascular risk factors including:
 - Dyslipidemia;
 - Hypertension;
 - Family history of coronary artery disease;
 - Type 1 or Type 2 diabetes mellitus.
- Other cardiovascular disease, including:
 - Congestive heart failure;
 - Peripheral arterial disease;
 - Cerebrovascular disease (carotid endarterectomy/carotid stenting, prior stroke, transient ischemic attack).

In addition, the status of diabetes mellitus at baseline and pre-diabetes at baseline will be derived using the following definitions:

Diabetes mellitus:

- Type 1 or Type 2 diabetes reported in medical history or as an adverse event before baseline (ie, before the first IMP intake or randomization for non-treated patients) (using company MedDRA query [CMQ] "Type 1 or Type 2 diabetes" as detailed in Appendix B, Table 11)
- And/or HbA_{1c} \geq 6.5% at baseline (V3) (or at V1 if V3 is not available)
- And/or 2 values of fasting blood glucose $\geq 126 \text{ mg/dL}$ (7.0 mmol/L) (at V1 and V3)
- And/or Use of anti-diabetic medication before baseline with a confirmed diagnosis per the external diabetes experts* (in case a partial start date for a given medication precludes determining whether it started prior or after baseline, the diabetes status will not consider anti-diabetic medications for the concerned patients).

* Patients classified as diabetic based only on the use of anti-diabetic medication before baseline will be reviewed in a blinded manner by external experts in diabetology. The individual Diabetes cases will be reviewed based on available information (e.g., medical history, concomitant medications, concomitant AEs, laboratory data, including complementary investigations as relevant). If the diabetic mellitus status is not confirmed, the patients will be classified as pre-diabetes or normoglyceamic according to the definitions below.

Pre- diabetes:

- Specific terms (CMQ "impaired glucose control" as detailed in Appendix B Table 12) reported in the medical history or as an adverse event before baseline (ie, before the first IMP intake or randomization for non-treated patients);
- And/or HbA1c \geq 5.7% and < 6.5% at baseline (V3) (or at V1 if V3 is not available)
- And/or two values of fasting glucose (at V1 and V3) ≥100 mg/dL (5.6 mmol/L) but no more than one ≥126 mg/dL (7.0 mmol/L).

Normoglyceamic

Patients not fulfilling either of the above criteria, will be classified as normoglyceamic at baseline.

Disease characteristics at baseline

Specific disease history includes:

- Information on index qualifying ACS event: number (%) of patients with elevated cardiac biomarkers (troponin I or T, or CKMB); with resting ECG changes consistent with ischemia or infarction (ST depression, ST elevation, T wave inversion, pathological Q waves, new tall R wave) and additional evidence of obstructive coronary disease (evidence of myocardial or infarction by perfusion imaging, regional wall motion abnormality, epicardial coronary artery stenosis ≥70%, need for revascularization [percutaneous coronary intervention (PCI) or coronary artery bypass graft surgery (CABG)] related to index ACS event);
- The index ACS subtype:
 - STEMI: elevated cardiac biomarkers (Troponin I or T, and/or CKMB) and new or presumed new ST elevation
 - NSTEMI: elevated cardiac biomarkers (Troponin I or T, and/or CKMB) and No new or presumed new ST elevation
 - UA: No Troponin I or T elevated, and No CKMB elevated, and "Resting ECG changed consistent with ischemia or infarction AND additional evidence of obstructive coronary disease" (ie, any combination of responses to questions "B" on the electronic case report form [e-CRF])
- Time from index ACS event to randomization (in weeks and in months), quantitatively and in category <2, ≥2 to <4, ≥4 to <6, ≥ 6 months
- Revascularization procedure associated with the index ACS event (PCI or CABG)
- Time from the revascularization procedure to randomization (in weeks and in months)
- New cardiovascular events occurring during the run-in period, selected using a list of preferred terms (PTs) from CMQ or standardized MedDRA query (SMQ).

Other baseline characteristics

Other baseline characteristics include weight in kilograms (quantitative variable), and body mass index (BMI) in kg/m² (quantitative and qualitative variable: $<30, \geq 30$).

Lipid parameters, HbA_{1c} (quantitative and qualitative variable: <5.7 %, ≥ 5.7 to <6.5%, ≥ 6.5 %) and hs-CRP (quantitative and qualitative variable: <2, ≥ 2 mg/L) at baseline will be also summarized by treatment group. Lipid parameters are total cholesterol (TC), LDL-C, non HDL-C, HDL-C, fasting triglycerides (TG), Apo A-1, Apo B, and lipoprotein (a) (Lp (a)).

For lipid parameters, both quantitative and qualitative variables will be considered, with the following categories:

- LDL-C: <70, ≥70 to <80, ≥80 to <100, ≥100 to <130, ≥130 to <160, ≥160 to <190, ≥190 mg/dL (ie, <1.81, ≥1.81 to <2.07, ≥2.07 to <2.59, ≥2.59 to <3.37, ≥3.37 to <4.14, ≥4.14 to <4.91, ≥4.91 mmol/L)
- HDL-C: $<40, \geq 40 \text{ mg/dL}$ (ie, $<1.04, \geq 1.04 \text{ mmol/L}$),
- Non-HDL-C: <100, ≥100 to <110, ≥110 to <130, ≥130 to <160, ≥160 to <190, ≥190 to <220, ≥220 mg/dL (ie, <2.59, ≥2.59 to 2.84, ≥2.84 to <3.37, ≥3.37 to <4.14, ≥4.14 to <4.91, ≥4.91 to 5.69, ≥5.69 mmol/L)
- Fasting TG: <150, ≥150 to <200, ≥200 mg/dL (ie, <1.7, ≥1.7 to <2.3, ≥2.3 mmol/L), category ≥150 mg/dL (ie, ≥1.7 mmol/L [mixed dyslipidemia]) will be also displayed,
- Lp (a): <30, ≥30 to <50, ≥50 mg/dL (ie, <0.3, ≥0.3 to <0.5, ≥0.5g/L), category ≥30 mg/dL (ie, ≥0.3 g/L) will be also displayed
- Apo B: <75, ≥ 75 to <90, ≥ 90 mg/dL (ie, <0.75, ≥ 0.75 to <0.9, ≥ 0.9 g/L)

In addition the number (%) of patients not adequately controlled at baseline as per protocol definition will be described:

- LDL-C ≥70 mg/dL (1.81 mmol/L) or Apo B ≥80 mg/dL (0.8 g/L) or non-HDL-C ≥100 mg/dL (2.59 mmol/L)
- LDL-C \geq 70 mg/dL (1.81 mmol/L)
- Apo B \geq 80 mg/dL (0.8 g/L)
- Non-HDL-C \geq 100 mg/dL (2.59 mmol/L)

Any technical details related to computation, dates, and imputation for missing dates are described in Section 3.5.

3.1.2 Prior or concomitant medications

All LMTs taken within 1 month before screening visit V1 and until the end of the study, are to be reported in 1 of the following specific case report form pages:

- Previous and concomitant statin drugs;
- Previous and concomitant medications lipid lowering drugs (other than statins);

Patients on chronic use of statin (ie, on any statin for at least 3 months prior to the index ACS event) and the reasons for any modification in the statin regimen post-randomization are to be reported on the following specific page:

• Additional statin information

Other concomitant medications taken since informed consent, including cardiovascular medications are to be reported on the following specific page:

• Concomitant medications (all other than statin and other than lipid lowering drugs).

All medications will be coded using the World Health Organization-Drug Dictionary (WHO-DD) using the version currently in effect at Sanofi at the time of database lock.

- Prior medications are those the patient used within 1 month before screening visit V1 and prior to first investigational medicinal product (IMP) injection. Prior medications can be discontinued before first administration or can be ongoing during treatment phase;
- Concomitant medications are any treatments received by the patient concomitantly to the IMP, from first IMP injection to the last double-blind injection +70 days. A given medication can be classified both as a prior medication and as a concomitant medication. Concomitant medications do not include medications started during the post-treatment period (as defined in the observation period in Section 3.1.4);
- Post-treatment medications are those the patient took in the period starting the day after the concomitant medication period up to the end of the study.

For patients randomized but not treated, medications will be categorized as prior medications or post-treatment medications according to the intake dates in relation to the date of randomization.

The following medications of specific interest will be also selected using specific coding's list:

- Aspirin or oral ADP receptor antagonists
- Injectable anticoagulants (UFH or LMWH or Bivalirudin or Selective Factor Xa inhibitor)
- Thrombolytic
- Specific oral anticoagulant
- Anti-diabetic drugs (insulin, oral anti-diabetic, other non-oral anti-diabetic)
- ACE-inhibitor or angiotensin receptor blocker
- Beta blocker

- Calcium channel blocker
- Diuretics
- Nitrates
- NSAIDs (excluding aspirin)

Any technical details related to computation, dates, imputation for missing dates are described in Section 3.5.

3.1.3 Efficacy endpoints

3.1.3.1 Primary efficacy endpoint(s)

The primary efficacy endpoint is the time from randomization to first occurrence of 1 of the following clinical events, as determined by the CEC:

- CHD death (including "undetermined causes of death" as per the CEC);
- Any non-fatal MI;
- Fatal and non-fatal ischemic stroke (including "stroke not otherwise specified" as per the CEC);
- Unstable angina requiring hospitalization.

The rules to determine the components and the date of the event that will be considered in the analyses of the primary efficacy endpoint are detailed in Appendix C.

If none of these events is observed at the time of the analysis cut-off date (final or interim, depending on the timing of the analysis, see Section 3.4.4.1 and Section 4 for details), the patient will be right-censored at the date of last contact when information on efficacy endpoints (presence or absence) has been retrieved, or at the date of death, or at the cut-off date/CSED, whichever comes first.

The last information on efficacy endpoint (presence or absence)" will be the latest date among:

- The date of last visit performed with "endpoints events" e-CRF page completed.
- The "Date of last information on efficacy endpoint (presence or absence)" reported in the visit e-CRF pages during the course of the study.
- The "Date of last information on efficacy endpoint (presence or absence)" reported at the end of the study for all patients (this information can also be completed during the course of the study for "lost-to-follow-up" patients, patients who discontinued the follow-up, and patients who died).

In case of no information on the presence or absence of efficacy endpoint, nor on death at time of database extraction for the interim analyses, the censoring date will be the randomization date (eg, for patients randomized but having not reached the Month 1 visit yet).

Handling of missing or incomplete dates

In the exceptional circumstances when the exact date of occurrence of the outcome event has not been established (day and/or month missing), the date will be imputed as follows:

Table 4 - Imputation of incomplete date of events composing the primary efficacy outcome

Type of event	Imputed date
	Only the day is missing
Death	The latter of the last contact date + 1 day and the 1 st day of the month.
Other primary endpoint component (CHD event or ischemic stroke)	The latter of the randomization date and the 1^{st} day of the month.
	Day and month are missing
Death	The latter of the last contact date + 1 day and January 1 st of the year.
Other primary endpoint component (CHD event or ischemic stroke)	The latter of the randomization date and January 1 st of the year.

CHD = coronary heart disease

3.1.3.2 Secondary efficacy endpoint(s)

Clinical events assessed in the analyses are those determined by the CEC. Events suspected by the investigator but not confirmed by the CEC will not be part of the outcomes. CHD death outcome will include deaths for causes that could not be determined by the CEC (adjudicated as "Undetermined cause of death"). Similarly, fatal and non-fatal ischemic stroke outcomes will include fatal and non-fatal strokes for causes that couldn't be determined by the CEC (adjudicated as "Stroke not otherwise specified").

Rules for censoring date and for imputation of incomplete dates of events will be the same as for the primary efficacy endpoint, for all secondary efficacy endpoints with the exception of the analyses of the time to CHD death, the time to CV death and of the time to all-cause mortality for which the censoring date will be defined as the earliest date among the "date of last known alive or Date of death" and the cut-off date/CSED.

The "date of last known alive or Date of death" will be the latest date among:

- The date of last visit performed;
- The "Date of last known alive or Date of death" reported in the visit e-CRF pages during the course of the study;
- The "Date of last known alive or Date of death" reported at the end of the study for all patients (this information can also be completed during the course of the study for "lost-to-follow-up" patients, patients who discontinued the follow-up and patients who died);

• The latest date among these dates, the last IMP injection date, the date of adverse events, the date of CV events, the date of death and the date of laboratory samples will be considered.

In case at time of database extraction for the interim analyses, only the randomization date is available, then the censoring date will be the randomization date.

3.1.3.2.1 Main secondary endpoint(s)

- Time from randomization to first occurrence of any CHD event (major CHD event, unstable angina requiring hospitalization, ischemia-driven coronary revascularization procedure);
- Time from randomization to first occurrence of any major CHD event (CHD death, nonfatal MI);
- Time from randomization to first occurrence of any CV event (any non-fatal CHD event, any CV death, and non-fatal ischemic stroke);
- Time from randomization to first occurrence of all-cause mortality, non-fatal MI, non-fatal ischemic stroke;
- Time from randomization to CHD death;
- Time from randomization to CV death;
- Time from randomization to death (all-cause mortality).

3.1.3.2.2 Other secondary efficacy endpoint(s)

- Component of the primary endpoint considered individually:
 - Time from randomization to first occurrence of any non-fatal MI;
 - Time from randomization to first occurrence of fatal or any non-fatal ischemic stroke;
 - Time from randomization to first occurrence of any unstable angina requiring hospitalization.
- Time from randomization to first occurrence of any ischemia-driven coronary revascularization procedure;
- Time from randomization to first occurrence of any congestive heart failure requiring hospitalization.

3.1.4 Safety endpoints

Following injections are considered as double-blind IMP injections:

• For patients randomized in the placebo group: any injection from double-blind kits;

• For patients randomized in the alirocumab group: any injection from double-blind kits excepted placebo injections given to maintain the blind in case of 2 consecutive LDL-C values <15 mg/dL.

Of note potential additional training injections after randomization using training injection kits will not be taken into account.

The period of safety observation starts from the time when the patient gives informed consent and is divided into three periods:

- PRE-TREATMENT period: defined from the signed informed consent up to the first dose of double-blind IMP injection;
- Treatment-emergent adverse event (TEAE) period: defined as the time from the first dose of double-blind IMP injection to the last dose of double-blind IMP injection +70 days (10 weeks), (as residual effect of treatment is expected until 10 weeks after the stop of double-blind IMP).

The TEAE period will include:

- The TREATMENT period defined as the time from the first dose of double-blind IMP up to the day of last dose of double-blind IMP injection +21 days, as serum concentration of alirocumab >10 μ g/mL is expected for approximately 21 days following administration of 150 mg, and because throughout the previous studies it was observed that when alirocumab concentrations declined below this concentration, decrease in effect on LDL-C is observed.
- The RESIDUAL TREATMENT defined as the time from the day of last dose of double-blind IMP injection +22 days up to the day of last dose of double-blind IMP injection +70 days (10 weeks).
- POST-TREATMENT period: defined as the time starting the day after the end of the TEAE period.

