### **Conclusion on the benefit risk assessment with alirocumab**

Based on the clinical data available to date, treatment with alirocumab has demonstrated a significant LDL-C lowering effect and was generally well tolerated in a population of patients with non-familial hypercholesterolemia or with heterozygous familial hypercholesterolemia. The efficacy on LDL-C was associated with consistent results in total cholesterol, ApoB, non-HDL-C and ApoB/ApoA-1 ratio and a positive trend for HDL-C, TG and Lp (a). There was no evidence that alirocumab adversely affects other cardiovascular risk factors, eg, body weight, blood pressure, glucose, or CRP.

In terms of identified or potential risks with alirocumab, local injection site reactions were reported as well as rare cases of hypersensitivity reactions. Local injection site reactions were reported in both alirocumab and placebo treatment groups with no evidence of dose relationship. These AEs will be monitored in the Phase 3 program including this study. A substantial proportion of patients reached low LDL-C levels (<25 mg/dl [0.65 mmol/L]) with no safety signal identified to date. However, further monitoring for potential AEs associated with low LDL-C levels will be implemented. Although no particular signal related to CPK elevation and associated AEs (e.g., myalgia, rhabdomyolysis) was detected with the co-administration of alirocumab and statins over a maximum duration of 12 weeks, monitoring for such adverse events will continue for all the Phase 3 studies, including this study. An independent Data Monitoring Committee (DMC), dedicated to the EFC11570 study and identified as CV DMC, will meet periodically to review unblinded safety data. This CV DMC will have a close connection with the other independent DMC implemented for all Phase 3 studies evaluating the efficacy and safety of alirocumab on LDL-C (identified as Phase 3a DMC).

This CV outcome study is undertaken to demonstrate in patients who recently experienced an ACS event and who are not at their LDL-C goal despite an intensive lipid-lowering therapy that alirocumab 75mg Q2W or 75 mg Q2W / 150 mg Q2W provides an additional benefit with the reduction of CV events.

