### 10.6.3 Monitoring related to two consecutive LDL-C <25 mg/dL (0.65 mmol/L)

Patients who achieve 2 consecutive LDL-C levels <25 mg/dL (0.65 mmol/L) during the study will be monitored and managed as per [Appendix A](#) (any time after randomization) as the lower limit of safe and effective LDL-C lowering has not yet been established. An independent external physician(s) (also known as independent physician) will be notified by the central laboratory of 2 consecutive LDL-C <25 mg/dL (0.65 mmol/L). The independent physician will review the unmasked LDL-C values and patient safety data, in close collaboration with the dedicated member of the Phase 3a DMC (implemented for all Phase 3 studies evaluating the efficacy and safety of alirocumab on LDL-C). This dedicated Phase 3a DMC member will then transmit any information as necessary to the common member involved in both DMCs (CV DMC and Phase 3a DMC).

Please see [Appendix A](#) for an outline of the process.

Then at subsequent visits, specific actions can be undertaken depending on the alirocumab dose (down-titration or discontinuation) as follows:

- On dose of 150 mg Q2W: if LDL-C <25 mg/dL (including LDL-C <15 mg/dL) on 2 consecutive values, down-titration to 75 mg Q2W will be done in a blinded manner at the next visit. The patient will remain at the down titrated dose of 75 mg Q2W for the remaining duration of the study, unless patient meets criteria below. As described above, specific monitoring consisting of review of patient level listing will be implemented.
- On dose of 75 mg Q2W:
  - If LDL-C <25 mg/dL on 2 consecutive values but there are no 2 consecutive measurements < 15 mg/dL (i.e. no measurement < 15 mg/dL or only one occasional measurement < 15 mg/dL): study treatment with 75 mg Q2W will be continued but additional monitoring with review of individual patient profiles will be implemented, to further confirm the safety of low LDL-C levels. A site alert related to 2 consecutive LDL-C < 25 mg/dL (0.65 mmol/L) may be requested by the independent physician (after consultation with dedicated phase 3a DMC member)
  - If measured LDL-C <15 mg/dL on 2 consecutive measurements: study treatment with 75 mg Q2W will be discontinued at the next visit. In order to maintain the blind there will be blinded substitution to placebo injections for the remaining duration of the study

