3.1.4.1 Adverse events variables

Occurrence of adverse events (including serious adverse events [SAEs], and adverse events of special interest [AESIs]) are recorded from the time of signed informed consent until the end of study.

All adverse events will be coded to a "Lowest Level Term (LLT)", "Preferred Term (PT)", "High Level Term (HLT)", "High Level Group Term (HLGT)", and associated primary "System Organ Class (SOC)" using the version of MedDRA currently in effect at Sanofi at the time of the database lock.

Adverse event observation periods

• Pre-treatment adverse events are adverse events that developed or worsened or became serious during the pre-treatment period;

- Treatment-emergent adverse events are adverse events that developed or worsened or became serious during the treatment-emergent adverse event period;
- Post-treatment adverse events are adverse events that developed or worsened or became serious during the post-treatment period.

Adverse events of special interest

Adverse events of special interest (AESIs) are adverse events (serious or non-serious) that need to be monitored, documented, and managed in a pre-specified manner described in the protocol. In this study, AESI are the following (their complete descriptions are provided in the protocol):

- General allergic events, selected using SMQ "hypersensitivity" (broad and narrow) excluding the following preferred terms linked to local injection site reactions ("infusion site dermatitis", "infusion site hypersensitivity", "infusion site rash", "infusion site urticaria", "injection site dermatitis", "injection site hypersensitivity", "injection site rash", "injection site urticaria", and "injection site vasculitis")
- Local injection site reactions, selected using e-CRF specific tick box on the adverse event page
- ALT ≥3 ULN (if baseline ALT <ULN) or ALT ≥2 times the baseline value (if baseline ALT ≥ULN), selected using laboratory data
- Hemolytic anemia, selected using e-CRF specific tick box on the adverse event page and confirmed final diagnosis provided in the adverse event complementary form

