If any clinically significant signal is detected and need further characterization, additional analyses similar to Tier 1 analyses, will be provided.

Descriptive analysis of infrequent adverse events – Tier 3 events

All infrequent TEAEs (Tier 3) will be reported with descriptive statistics (n, %) and event rate per 100 patient year, without comparative statistics since with so rare event statistical comparisons are not meaningful and medical judgment should prevail.

Analysis of all treatment-emergent adverse events

The following TEAE summaries, including all TEAEs (common or not, Tier 1 or not) will be generated for the safety population.

- Overview of TEAEs, summarizing number (%) of patients with any:
 - TEAE;
 - Serious TEAE;
 - TEAE leading to death;
 - TEAE leading to permanent treatment discontinuation.
- All TEAEs by primary SOC, HLGT, HLT, and PT, sorted by the SOC internationally agreed order. The other levels (HLGT, HLT, PT) will be presented in alphabetical order;
- All TEAEs regardless of relationship and related to IMP by primary SOC, HLGT, HLT, and PT, sorted by the internationally agreed SOC order. The other levels (HLGT, HLT, PT) will be presented in alphabetical order;
- All TEAEs regardless of relationship and related to statin/other lipid lowering drug by primary SOC, HLGT, HLT, and PT, sorted by the internationally agreed SOC order. The other levels (HLGT, HLT, PT) will be presented in alphabetical order;
- All TEAEs by primary SOC and PT, sorted by the internationally agreed SOC order and by decreasing incidence of PTs within each SOC (in the alirocumab group). This sorting order will be applied to all other tables by SOC and PT of TEAEs, unless otherwise specified. The event rate per 100 patient-years (the number of patients with an event in question divided by total patient-years) will be provided for all TEAEs by SOC and PT. For a patient with event, patient-year is censored at time of first event; for patient without event, it corresponds to length of TEAE period;
- All TEAEs that occurred with HLT and PT incidence ≥2% in alirocumab group and at incidence at least 0.5% higher in alirocumab than placebo, by primary SOC, HLT, and PT;
- All TEAEs that occurred with incidence ≥5% in any treatment group, by primary SOC and PT, with event rate per 100 patient-years;
- All TEAEs by maximal severity (ie, mild, moderate, or severe), presented by primary SOC and PT.

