3.5 DATA HANDLING CONVENTIONS

3.5.1 General conventions

The following definitions/formulas will be used for computation of parameters.

Common study end date

The common study end date is defined as the date when 1613 patients have experienced at least 1 primary efficacy event or 24 months after the last date of randomization ex-China, whichever comes last.

Date of last dose of investigational medicinal product

The date of the last dose of IMP is equal to the last date of administration reported on the IMP administration case report form page, or missing if the last administration date is unknown. For patients on the alirocumab arm who will switch to placebo injection due to blinded treatment discontinuation, the date of last administration reported associated to an active injection will be considered.

Renal function formulas

eGFR value will be derived using the Modification of the Diet in Renal Disease (MDRD) equation:

175 x (creatinine in μ mol/L / 88.4)^{-1.154} x (age in years)^{-0.203} (x 0.742 if female, x 1.212 if race is "black or african american").

Lipids variables, laboratory safety variables, hs-CRP

For data below the lower limit of quantification (LLOQ)/limit of linearity, half of the lower limit value (ie, LLOQ/2) will be used for quantitative analyses. For data above the upper limit of quantification (ULOQ) / limit of linearity, the upper limit value (ie, ULOQ) will be used for quantitative analyses.

The above rules won't be applied for the calculated LDL-C and non-HDL-C when HDL-C value is below the LLOQ. The value of LLOQ/2 for HDL-C will be used to obtain the non-HDL-C and calculated LDL-C used for quantitative analyses.

Below is an example of data for a dummy patient reported in the database, with the values that will be used in quantitative analyses for each parameters.

Parameter	Value reported in the database	Value used in the analysis	
 TC	255 mg/dL	255 mg/dL	_
HDL-C	<10 mg/dL	5 mg/dL	
Calculated LDL-C ^a	<221 mg/dL	216 mg/dL	
NON-HDL-C	<255 mg/dL	250 mg/dL	
TRIG	172 mg/dL	172 mg/dL	

Table 7 - Example of lipid data for a dummy patient

a Friedewald formula for calculated LDL-C (when lipid expressed in mg/dL: LDL-C=NON-HDL-C-0.2*TG)

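### Adverse-event tables given as number (%) only use a window that closes early for alirocumab patients switched to blinded placebo, which lowers alirocumab percentages slightly

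*SAP*

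**What the plan says.** SAP 3.1.4 defines the counted injections separately by arm.

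- Placebo arm: "For patients randomized in the placebo group: any injection from double-blind kits".
- Alirocumab arm: "any injection from double-blind kits excepted placebo injections given to maintain the blind in case of 2 consecutive LDL-C values <15 mg/dL".

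SAP 3.4.3 and Protocol 11.3.2 and 11.4.1 repeat the alirocumab exclusion. The TEAE period runs from the first to the last such injection plus 70 days. For a switched patient SAP 3.5.1 fixes the last dose accordingly: "the date of last administration reported associated to an active injection will be considered". Injections do not stop at that point. Protocol 10.6.3 says "there will be blinded substitution to placebo injections for the remaining duration of the study". Adverse events also go on being collected; under SAP 3.1.4.1 they "are recorded from the time of signed informed consent until the end of study".

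SAP 3.4.5.1 uses the whole safety population of each arm as the denominator of adverse-event percentages. One of its tables lists terms with at least 2% incidence on alirocumab and "at incidence at least 0.5% higher in alirocumab than placebo".

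**The concern.** A switched alirocumab patient and a placebo patient may inject from blinded kits on the same schedule to the end of the study, yet contribute windows of very different length. Shortening a window can remove a first event from the numerator but does not remove the patient from the denominator, so a crude alirocumab percentage can only fall.

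At stake are displays that readers use first: how many patients had any, a serious or a fatal TEAE, and which terms are shown as more frequent on alirocumab. In the filter table the affected percentage also decides what appears. A rate printed beside the selected terms cannot bring back a term that was filtered out.

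**Working it through.** **Step 1: which displays are exposed.** The documents give no figure for the imbalance, so there is none to reproduce. I sorted the planned safety displays by whether they account for window length.

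| Display | Measure planned | Exposed? |
|---|---|---|
| Tier 1 events (SAP 3.4.5.1) | n (%), rate per 100 patient-years, Cox HR censored at end of TEAE period | No |
| Tier 2, common terms | n (%), rate, Cox HR | No |
| Tier 3, infrequent terms | n (%), rate | No |
| All TEAEs by SOC and PT; terms at 5% or more | n (%), rate | No (the 5% selection itself is crude) |
| Deaths (SAP 3.4.5.2) | n (%) to the common study end date | No, not cut at the TEAE window |
| TEAE overview | n (%) | Yes |
| Filter at 2% and +0.5 points | n (%) | Yes |
| SAEs; TEAEs leading to discontinuation | no rate specified | Yes |
| PCSA incidences (SAP 3.4.5, 3.4.5.3, 3.4.5.4) | n (%) of patients assessed in the TEAE period | Yes |
| Hemorrhagic stroke per CEC (SAP 3.4.6) | n (%) in the TEAE period | Yes |

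The last row matters more than its place in the SAP suggests. Hemorrhagic stroke is outside the primary endpoint (Protocol 9.1.6.3) and is not a Tier 1 grouping. Suspected endpoint events are generally not reported as adverse events (Protocol 10.4.3; SAP 3.4.6). I found no planned rate, hazard ratio or post-treatment table that would recover a non-fatal hemorrhagic stroke occurring after the window closes.

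**Step 2: size for crude percentages.** Inputs:

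- Share switched, f: not in the documents; assumed 1% to 8%.
- Switch time: assumed month 8 to 12. The visit schedule allows month 4 at the earliest, after low values at months 1 and 2.
- Follow-up, L: 33 months (assumed), or 40.4 months. The latter is the mean follow-up from the monthly accrual rates in SAP Table 1, with mid-month entry and study end at month 64.
- True incidence, p: 10% over L in both arms, constant hazard, no treatment effect (assumed).

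Formulas:

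- Hazard λ = −ln(1 − p)/L.
- Window of a switched patient t = switch month + 70/30.4375 = switch month + 2.30.
- Incidence within that window p_t = 1 − exp(−λt).
- Crude alirocumab incidence = (1 − f)p + f·p_t, so the deficit is f(p − p_t).

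For L = 33, λ = 0.10536/33 = 0.003193 per month.

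- 1% switched at month 12: t = 14.30, p_t = 4.46%, deficit 0.01 × (10 − 4.46) = 0.06 points, so 9.94% against 10%.
- 8% switched at month 8: t = 10.30, p_t = 3.235%, deficit 0.08 × (10 − 3.235) = 0.54 points, so 9.46% against 10%.

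For L = 40.4, λ = 0.10536/40.4 = 0.002608 per month.

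- 1% at month 12: p_t = 3.66%, deficit 0.06 points.
- 8% at month 8: p_t = 2.65%, deficit 0.59 points.

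With 5% switched at month 8 to 12, the deficit is 0.28 to 0.34 points (L = 33) or 0.32 to 0.37 points (L = 40.4).

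**Step 3: other incidences.** These use the full accrual pattern. At 2% incidence the deficit is at most 0.17 points, even with 10% switched at month 4. At 25% incidence with 5% switched, it is 0.76 points (month 12) to 1.03 points (month 4).

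**Step 4: person-time on the same windows.** Expected person-time is p/λ for an unswitched patient and p_t/λ for a switched one. For L = 33 and 8% switched at month 8, these are 31.32 and 10.13 months. The arm's rate is 0.09459/(0.92 × 31.32 + 0.08 × 10.13) = 0.09459/29.63 = 0.00319, which equals λ. The rate ratio under no effect is 1.000, here and in every other scenario run.

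**The case against.** A reader might infer that the safety comparison as a whole is biased. The documents do not support that. Tiers 1 and 2, which are the analyses meant to compare the arms, have rates and hazard ratios on the truncated window. Any term at 2% of about 9,300 patients is about 186 patients, far above the Tier 2 threshold, so a term that misses the +0.5-point filter still appears in Tier 2, where one table is ranked by hazard ratio. The filter table is an extra display, not the only one.

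A reader might also infer that post-switch harms vanish, or that only alirocumab windows can end early. Neither is right. Post-treatment adverse events and SAEs are tabulated (SAP 3.4.5.1) and deaths run to the common study end date, so most events are moved rather than lost; non-fatal hemorrhagic stroke is the exception I found. Ordinary permanent discontinuation closes the window in both arms. What is specific to alirocumab is closure while kit injections continue.

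Third, a high switch share might be read into the protocol's remark "A substantial proportion of patients reached low LDL-C levels". That remark concerns values below 25 mg/dL in earlier studies, whereas the switch needs two values below 15 mg/dL. For this trial the protocol (Section 4, rationale for protocol design) expects few patients even below 25.

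Finally, the excluded time begins more than 70 days after the last active dose, when residual effect is no longer expected. An on-drug window is a legitimate, prespecified choice, and a common window used as the main display would dilute a true on-drug excess. The period at low LDL-C also has its own two-step analysis, repeated at 15 mg/dL.

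All of this stands. It narrows the point to the displays that give number (%) only; it does not make their windows comparable.

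**Conclusion.** The point holds for a limited set of displays: the TEAE overview, the filter table, the SAE and discontinuation tables, the PCSA incidences, and hemorrhagic stroke per CEC. For tables with the whole safety population as denominator, the direction follows from the definitions. For PCSAs the denominator is patients assessed in the window, so the same direction is expected but is less strict.

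The size is unknown because the switch share is not given. At 1% switched it is negligible, about 0.06 points on a 10% event. At 8% switched at month 8 it is 0.54 to 0.59 points, as large as the filter's own threshold: a term would then need a true excess of roughly 1 point (0.5 + 0.54 = 1.04) to be listed. For rare terms the shift stays small throughout. These figures rest on a constant hazard, no true effect, and assumed switch times and follow-up.

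Person-time corrects the unequal windows only. Closure is triggered by very low LDL-C, so the censoring may still be informative. That is the reason for one sensitivity analysis on a common window.

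**What to change.** 1. Add event rates per 100 patient-years, or hazard ratios censored at the end of the TEAE period, to the TEAE overview, the filter table, the SAE and discontinuation tables, the PCSA incidences, and the SAP 3.4.6 display of hemorrhagic stroke.
2. Apply the 0.5-point selection rule to an exposure-adjusted measure, with the threshold restated on that scale before unblinding.
3. Keep the active-drug window as the main display.
4. Add, as a sensitivity analysis only, the same tables on one window for both arms: first injection to last injection from any double-blind kit plus 70 days.

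The data for item 4 are already collected. Sites are unaware of the switch, so full adverse-event recording continues. After a permanent stop it runs to 6 months past the early end-of-treatment visit (Protocol 10.4.4), longer than the 70 days needed.

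The cost is SAP wording, a few extra columns and one extra set of tables. Off-drug time enters the alirocumab arm in the sensitivity analysis only. No treatment rule changes.
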